APPENDIX 3. OVERVIEW OF RESEARCH SITES

21

GLOSSARY OF ABBREVIATIONS

CLOCS	Cancer Loyalty Card Study
HSR1	High Street Retailer 1
HSR2	High Street Retailer 2

KEYWORDS

Ovarian Cancer
Epidemiology
Observational Study
Risk Assessment

STUDY SUMMARY

TITLE Cancer Loyalty Card Study (CLOCS)

DESIGN Observational, retrospective case-control study

AIMS The CLOCS aims to investigate whether or not women have distinctive self-management behaviours prior to seeing their doctor with symptoms that are associated with ovarian cancer.

OUTCOME MEASURES The primary outcome of the CLOCS will be to define the time by which the cases and controls are statistically significantly different in their purchase behaviours leading up to diagnosis on a population level.

The secondary outcome of the CLOCS will be defining a purchase threshold as an “alert” about cancer symptoms in individuals and determining the predictive utility of purchasing behaviours in the early detection of ovarian cancer. Exploratory analyses will include longitudinal analyses, frequency of purchases and an unbiased analysis of other purchase categories.

POPULATION At least 1000 women in the UK (500 ovarian cancer cases and 500 controls)

ELIGIBILITY Women, at least 18 years old, who own at least one participating high street retailer loyalty card are eligible to join the CLOCS. Among these women, those who have been diagnosed with ovarian cancer can join the CLOCS as cases, and those who have no prior ovarian cancer diagnosis are eligible to join as controls.

DURATION 3 years

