2. STUDY OBJECTIVES

- 2.1** The primary aim of the CLOCS will be to define the time by which participants with ovarian cancer are statistically significantly different in their purchase behaviours leading up to date of diagnosis, compared with purchase behaviours of participants without ovarian cancer.
- 2.2** The secondary aim of the CLOCS will be to define a purchase threshold as an “alert” about cancer symptoms in individuals and determining the predictive utility of purchasing behaviours in the early detection of ovarian cancer.

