6. OVARIAN CANCER RISK FACTOR AND SYMPTOM DATA COLLECTION

6.1 Upon choosing to participate in the CLOCS, participants will also complete a questionnaire requesting information about well-established ovarian cancer risk factors and symptoms.

6.1.1 The well-established risk factors include ethnicity, marital status, body mass index, age at menarche, menopausal status, age at menopause, parity,

breastfeeding, hysterectomy, tubal ligation, cancer history, endometriosis, aspirin use, oral contraceptive use, hormone replacement therapy (HRT), family history of ovarian and breast cancers, vaping, and cigarette smoking

- 6.1.2** The questionnaire asks participants about the symptoms experienced (if any) and number of visits to the general practitioner in the year leading up to cancer referral or diagnosis.
- 6.1.3** The questionnaire asks participants about which food and pharmacy stores they shop at regularly, at which stores they own a loyalty card, frequency of use of those loyalty cards, where they heard about the study (for controls only), and the number of people in their household (for adjustment in analysis).
- 6.1.4** In order to understand the impact of COVID-19 on purchase history and ovarian cancer diagnosis delays, the questionnaire includes a question about whether participants have had Covid19 (diagnosed and recovered/diagnosed and still ill/suspected but not formally diagnosed/did not have covid)
- 6.1.5** For participants diagnosed with ovarian cancer (considered cases), this will occur in the clinic or at home if they choose to complete it at home.
- 6.1.6** For participants who do not have ovarian cancer (considered controls), this questionnaire will be completed online.
- 6.2** For participants with ovarian cancer, there will be a separate questionnaire to be completed by their recruiting clinician or member of their healthcare team regarding information about ovarian cancer diagnosis date, type, grade, stage, and surgical outcome, if any. If a patient chooses to complete the questionnaire at home, a member of the clinical care team will send their completed clinical questionnaire with them.
- 6.3** The clinical care teams will not keep a copy of the CLOCS participant consent form.

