- 7.7** The date of recruitment as written on the questionnaire and consent forms will be the final date of purchase data requested by the CLOCS team. At most, up to 6 years of participants' past purchasing data prior to the date of recruitment will be shared with the CLOCS team, depending on the high street retailer's records and when the participant obtained the loyalty card. This includes data about the items purchased (e.g. paracetamol), when (i.e. date of purchase) and where they were purchased (i.e. store postcode). This will not include information on NHS prescriptions or any personally identifiable information, e.g. full name, postcode, ethnicity.
- 7.8** The CLOCS team will save the past purchase data to a secure and encrypted server based at Imperial College London.

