9.2 Data analysis

- 9.2.1 The statistical software R will be used for all data analyses.
- 9.2.2 We will define the time prior to diagnosis by which the cases become statistically significantly different in their purchase behaviours to the controls.
- 9.2.3 We will explore this using a multivariable, conditional logistic regression model with ovarian cancer as the outcome and "purchase proportion" at different times prior to diagnosis as the exposure, adjusting for stage and histology and other potentially confounding variables collected from the risk factor questionnaire.
- 9.2.4 We will compare the proportions of purchases in cases to controls, stratified by risk quintiles defined by the epidemiological risk model (estimated n=86 per quintile) or by histology (with expected proportions of high grade serous cases n=335; mucinous cases n=70; endometrioid n=35; clear cell n=35, and low grade serous n=25).
- 9.2.5 We will estimate the predictive values (ROC AUC, PPV, NPV, specificity and sensitivity) of this "early diagnosis" test for each stratum.
- 9.2.6 We will conduct exploratory analyses investigating other methods leveraging the auto correlation in the longitudinal data. Specifically, we will investigate the frequency of purchases and purchase trajectories, to identify purchase patterns (e.g. increasing purchases before diagnosis, purchase peaks, etc.), that are indicative/predictive of the individual disease onset.

- 9.2.7** Using longitudinal approaches, we will investigate if these patterns help in predicting the time-to-onset.
- 9.2.8** This type of approach could be generalised using other purchase categories for further hypothesis generation.

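### The summary aim concerns behaviour before a woman sees her doctor, but the main analyses count back from diagnosis and none separates purchases made before and after first consultation

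*Combined protocol and SAP*

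**What the plan says.** The aim in the Study Summary is set at the point of first medical contact: whether "women have distinctive self-management behaviours prior to seeing their doctor with symptoms that are associated with ovarian cancer". The Background (1.1) supports that framing. It describes women who put off going to the GP and treat themselves with shop-bought remedies instead.

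The rest of the plan is set at diagnosis:

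- The primary outcome in the same summary concerns "purchase behaviours leading up to diagnosis on a population level".
- Aim 2.1 concerns "purchase behaviours leading up to date of diagnosis, compared with purchase behaviours of participants without ovarian cancer".
- Section 9.2.2 reads "We will define the time prior to diagnosis by which the cases become statistically significantly different in their purchase behaviours to the controls", and the regression in 9.2.3 takes the purchase proportion "at different times prior to diagnosis as the exposure".

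On primary care, the questionnaire (6.1.2) asks for symptoms and the "number of visits to the general practitioner in the year leading up to cancer referral or diagnosis". The clinical form (6.2) lists the diagnosis date. Neither description includes a date of first consultation or of referral. Purchases are individually dated and run up to recruitment (7.7). On prescriptions, 7.7 states: "This will not include information on NHS prescriptions".

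**The concern.** Between the first GP visit for symptoms and the diagnosis, a woman is already in contact with her doctor. What she buys then cannot prompt that first visit. It may also reflect the visit itself, through advice, worry, or a change between shop-bought and prescribed medicines. Prescriptions are not captured, so such a change could raise or lower the recorded purchases.

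The plan counts these purchases together with those made before the visit. Two things are at stake. A reader who takes the summary aim at face value could read the reported time as self-management before consulting. And the alert threshold, with the sensitivity, specificity, PPV, NPV and AUC planned for it, could draw partly on purchases that came after the event it is meant to precede.

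**Working it through.** The plan has no figure to reproduce. It gives no alpha, power, effect size, purchase rate, lead time or consultation-to-diagnosis interval.

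**Step 1. Time anchors side by side**

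- Study Summary aim: before seeing the doctor.
- Study Summary primary outcome, 1.2, 2.1, 9.2.2 and 9.2.3: before diagnosis.
- 2.2, 9.2.4 and 9.2.5: no time anchor of their own.
- 9.2.6-9.2.7: before diagnosis in one example, otherwise onset, which is not defined. Diagnosis is the only disease date that section 6 lists.

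Aim 2.1 and its analysis agree with each other. The mismatch is between the summary aim and everything that would have to answer it.

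**Step 2. Can the listed data make the split?** The purchases are dated, so they could be cut at any date. A number of visits does not give that date, and section 6 describes no other field that does.

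**Step 3. What the missing date means for a lead time.** Let T be the months before diagnosis at which cases diverge, and C the months before diagnosis of first consultation (one common value, for simplicity). Then

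- lead before consultation = max(T - C, 0)
- difference from the reported time = min(T, C), which is never negative.

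Neither T nor C is in the documents, so all values below are assumed (months).

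| T | C = 0 | C = 1 | C = 3 | C = 6 | C = 12 |
|---|---|---|---|---|---|
| 6 | 6 | 5 | 3 | 0 | 0 |
| 12 | 12 | 11 | 9 | 6 | 0 |

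Entries are the lead before consultation. With C = 0 the two readings coincide.

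**Step 4. Could purchases after consultation alone give a significant window?** Assume that nothing changes before consultation, that the proportion buying is p0 in controls and p1 in cases who have consulted, and that a share f of cases has consulted by that window. The case proportion is then pc = p0 + f(p1 - p0). Take n = 500 per group (the planned minimum), a two-sided 0.05 test and an unmatched approximation, with p̄ = (p0 + pc)/2:

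power = Φ{ [ (pc - p0) - 1.96·√(2p̄(1-p̄)/n) ] / √( [p0(1-p0) + pc(1-pc)]/n ) }

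Example: p0 = 0.10, p1 = 0.20, f = 0.5 gives pc = 0.15 and p̄ = 0.125. The numerator is 0.05 - 1.96 × 0.0209 = 0.0090, the denominator is 0.0209, the ratio is 0.43, and the power is 0.67.

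| p0 to p1 | f = 25% | f = 50% | f = 75% | f = 100% |
|---|---|---|---|---|
| 10% to 20% | 0.24 | 0.67 | 0.93 | 0.99 |
| 20% to 30% | 0.16 | 0.47 | 0.80 | 0.96 |
| 10% to 15% | 0.09 | 0.24 | 0.45 | 0.67 |

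This shows that the planned comparison can date a divergence when there is no pre-consultation signal. The absence of such a signal is assumed by construction, so the table says nothing about how likely that is.

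**Step 5. Reach.** If the windows in 9.2.3 turn out to be discrete, which the plan does not specify, a reader could look past the most recent ones in the time scan. That does not help the alert or its predictive values: 2.2 and 9.2.5 do not say which purchases enter them, and no cut is stated.

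**The case against.** The strongest reply is that the formal primary aim (2.1) is anchored on diagnosis, as are the primary outcome and the rationale in 1.2, and that 9.2.2-9.2.3 answer that aim. Only one sentence in the summary differs, and editing it would remove the mismatch. This stands as far as it goes: the primary analysis is not wrong for 2.1, and rewording is an acceptable remedy. But the Background's account of self-treatment in place of a GP visit makes the sentence more than a slip, and rewording alone would leave the alert unexamined.

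A reader might infer that the study will overstate its lead time. The documents do not support this. They state no lead time and promise none before consultation, and a time before diagnosis is correct for what 2.1 defines. It is too long only if read as time before consultation, and by an amount that cannot be computed.

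A reader might also infer that every analysis counts back from diagnosis, or that purchases after a first visit have no value for earlier detection. The first goes beyond 9.2.4-9.2.7, which give no anchor or refer to an undefined onset. The second is too strong. The goal in 1.2 and 2.2 is earlier diagnosis or detection, 6.1.2 allows for several GP visits, and a signal after the first visit might still shorten the remaining delay. That is a different use from the one in the summary aim.

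Two practical objections also stand. The first symptomatic visit may be hard to date when symptoms are vague. And the forms themselves are not in the text available for review, so a date field that section 6 does not describe cannot be ruled out.

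**Conclusion.** The point holds in a limited form. The planned result is a valid answer to aim 2.1, as time before diagnosis. It cannot be read as behaviour before a woman consults her doctor, which is what the summary aim asks about. The alert and its predictive values may be partly built on purchases by women who had already consulted.

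The size is unknown, because the documents give no consultation-to-diagnosis interval. The months and probabilities above rest entirely on assumed values and show direction and possibility only. The conclusion assumes that the forms collect no more dates than section 6 describes. If a consultation or referral date is already recorded, only the analysis needs to change.

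**What to change.** 1. Keep the diagnosis-anchored analysis as primary for 2.1.
2. If it is not already there, add the date of first symptomatic GP consultation or of referral, where known, to the case questionnaire (6.1.2) or the clinical form (6.2).
3. Add a supplementary analysis to 9.2.2-9.2.5 that drops each case's purchases after that date and applies the same shift to the matched control's index date. The plan must define that index date, which it does not do now.
4. Where the date is unavailable, drop the last 1, 3 and 6 months before diagnosis in turn, and describe these as assumed lags.
5. Apply the same cuts when deriving and evaluating the alert threshold.
6. Base any claim about pre-consultation behaviour or lead time on this analysis only. Otherwise, restate the summary aim as behaviour before diagnosis.

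The cost is one date on an existing form and one repeated analysis; the lagged version needs no new data. Fewer purchases near diagnosis remain usable. Most of the history is kept: a case recruited 2 years after diagnosis with the full 6 years of records has 6 - 2 = 4 years before diagnosis, and 3.5 years after a 6-month lag, though some records will be shorter. The consultation date will carry some recall error, and the reported lead time will probably be shorter.

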1. INTRODUCTION

1.1 BACKGROUND

The ten-year survival rate for epithelial ovarian cancer (EOC) is only 35% in the UK and is dramatically different for stage 1 disease (90%) compared with stage 3-4 (5-15%). Survival in the UK lags behind Europe; this is attributed partly to a delay in diagnosis [1]. Earlier detection of low-volume disease or earlier stage ovarian cancer will save lives [2].

EOC is a heterogeneous disease with different histological subtypes that show strikingly different molecular [3] and mutational profiles [4,5]. With the Ovarian

Cancer Association Consortium (OCAC), we have identified 34 common genetic polymorphisms contributing to polygenic risk [6–9]. Epidemiological risk factors provide a predictive model with a modest discriminatory power (AUC=0.65), improved slightly with polygenic risk (AUC=0.66) [10], and this model has been proposed to improve EOC detection with risk stratified screening [11].

EOC usually presents with vague and non-alarming symptoms. As a result, most women are diagnosed late when the cancer has already spread and the prognosis is poor. The most common symptoms associated with EOC are increased abdominal size, pelvic pain, abdominal pain and bloating, feeling full quickly and difficulty eating [12,13]. The major reasons for not presenting to the GP with symptoms such as these are “not wanting to waste the GP’s time” [14] and normalisation of these symptoms [15]. The persistence of a symptom, social influence and awareness encourage help-seeking behaviours in primary care [16]. However, few believe that their symptom(s) might be a sign of cancer [17]. Consequently, people might choose to self-manage their symptoms by using over-the-counter medication, and to seek advice from other sources, (pharmacists, family, internet), rather than a primary care physician.

1.2 RATIONALE FOR CURRENT STUDY

Approximately 7,400 new cases of ovarian cancer are diagnosed each year in the UK, and with over 4,000 women dying from the disease each year it is a particularly lethal form of cancer. The symptoms are not well known, are vague and non-specific and most women are diagnosed at a late stage when the cancer has already spread around the peritoneum with poor prognosis. Novel methods are needed to improve earlier detection and thereby improve survival from this disease. We hypothesise that a change in purchasing behaviour, primarily an increase in self-medication to treat these vague cancer symptoms, may provide a novel avenue for earlier diagnosis for cancer.

In this study we propose to use loyalty card data from two participating high street retailers (Boots and Tesco) to investigate purchase behaviour as an opportunity for cancer symptom surveillance. We aim to conduct a case-control study of women with ovarian cancer (cases) matched with women who do not have ovarian cancer (controls) and define the time by which the cases are statistically significantly different in their purchase behaviours leading up to date of diagnosis, compared with the control purchase behaviours.

2. STUDY OBJECTIVES

- 2.1** The primary aim of the CLOCS will be to define the time by which participants with ovarian cancer are statistically significantly different in their purchase behaviours leading up to date of diagnosis, compared with purchase behaviours of participants without ovarian cancer.
- 2.2** The secondary aim of the CLOCS will be to define a purchase threshold as an “alert” about cancer symptoms in individuals and determining the predictive utility of purchasing behaviours in the early detection of ovarian cancer.

3. STUDY DESIGN

Purpose and Design

The Cancer Loyalty Card Study (CLOCS) is addressing whether or not data already collected by high street retailers can detect significant changes in purchase behaviours of ovarian cancer patients prior to their diagnosis. We aim to conduct a case-control study of ovarian cancer patients matched with women who do not have ovarian cancer. We will recruit at least 500 recently diagnosed ovarian cancer patients and at least 500 healthy women as controls and collate up to 6 years of prior purchase data.

Recruitment

Women living with ovarian cancer and who own at least one of the participating high street retailer's loyalty cards will be recruited in a clinic by a member of their healthcare team where the study is open (recruitment sites listed in Part C).

Women, 18 years or older, living in the UK who have a loyalty card at the participating high street retailers will be recruited through the study website (www.clocsproject.org.uk) where data collection will be safeguarded using an encrypted web form that includes study consent and the self-report questionnaire. There will be a press release and social media about the study inviting loyalty card holders to visit the CLOCS website for more information and join the study. Any woman considering joining the study can contact the research team using the contact details on the information sheet.

Consent

Ovarian cancer patients will be given the information sheet and consent form in the clinic by a member of their healthcare team. They can take as much time as they need to read through the information sheet. If they choose to participate, they can complete the consent form whenever is convenient for them and return it to the CLOCS team in the freepost envelope provided to them in the clinic.

Alternative recruitment strategy during Covid-19 lockdown to minimise contact with patients
The research sites will be asked to identify the patients who may be eligible for the study using their records and contact them by phone to facilitate recruitment to CLOCS. During this process, the research nurse will read out the information sheet and ask participants if they wish to take part. If patients are interested in taking part, then they will complete the consent forms and the questionnaire on their behalf. They will take a copy of the completed questionnaire and the consent form and post the original to the CLOCS team using CLOCS freepost envelope and post the copy including the information sheet and privacy policy to the patients. Patients similar to the previous protocol can withdraw their consent at any stage of the study.

Women without ovarian cancer will be presented with the information sheet and consent form on the study website and can consent to participate online.

Methods

Consenting participants will complete a brief questionnaire about ovarian cancer risk factors, which will also be returned to the CLOCS team through the mail or on the website (healthy volunteers only). Participants with ovarian cancer will also have a clinical form for a member of their clinical team to complete in the clinic. This will be sent to the CLOCS team along with their consent and risk factor questionnaire in the freepost envelope. In order to adhere with participating high street retailers' policies, healthy volunteers will need to provide a photo ID and utility bill for ID verification. This is not required for participants with ovarian cancer because they will be recruited by a member of their care team in the clinic.

Two ovarian cancer patients have reviewed all questionnaires and CLOCS documents and expressed their approval. Women without ovarian cancer from the general UK population have also reviewed the risk factor questionnaire and expressed their approval saying the questionnaire is 'easy to understand' and 'straightforward'.

If participants consent to be re-contacted by the CLOCS team for future studies or for loyalty card detail clarification, they will provide either a contact email or phone number. There is no further action needed from participants once they complete their consent form and questionnaire (and clarify loyalty card details if necessary).

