5. PARTICIPANT RECRUITMENT AND CONSENT

The CLOCS will recruit loyalty card holders through advertisement of the study and through clinics around the UK where the CLOCS is open. Advertisement of the CLOCS will start with a press release introducing the study to the general population, inviting loyalty card holders to visit the CLOCS website for more information and possibly participate.

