5.1 RECRUITMENT OF WOMEN WITHOUT OVARIAN CANCER (CONTROLS)

Women without ovarian cancer will be recruited through the study website (www.clocsproject.org.uk) where data collection will be safeguarded using an encrypted web form that includes study consent and the self-report questionnaire. No clinical questionnaire is needed for control participants.

The online participation will take up to 15 minutes and data will be transferred immediately to the secure CLOCS server. The website approach was adopted as one of the outcomes of the proof-of-concept study. It aims to provide a transparent environment where potential participants can make informed decisions about participation in CLOCS, and the data risks are minimised using encryption. We have carefully designed the website to inform the general public about how we will process their data in CLOCS, how they can withdraw from the study if they wish to do so and use it as a platform to provide feedback as we progress in the larger CLOCS project. The research team will use several methods to recruit control participants to the study which will include a press release carried out by the project funders and the Imperial College London public engagement team, dissemination of study flyers and leaflets, and social media marketing techniques on Twitter and Facebook using paid advertisement and unpaid methods. The application of the social media recruitment methods will allow researchers to reach a larger cohort in the UK. The application of both paper-based and online recruitment methods will be carried out throughout CLOCS and will be recorded.

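### Cases come through open clinics and controls from the whole UK by web, yet section 9.2.3 draws on no listed direct measure of place or socioeconomic position, and section 9.2 leaves the store postcode unused

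*Combined protocol and SAP*

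**What the plan says.** **Source of cases.** Section 3 has cases "recruited in a clinic by a member of their healthcare team where the study is open". Section 5 describes this as recruitment "through clinics around the UK where the CLOCS is open". The COVID-19 contingency (section 5.3) replaces the visit with a telephone call but still runs through the participating sites.

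**Source of controls.** Section 3 says that women "living in the UK who have a loyalty card at the participating high street retailers will be recruited through the study website". Section 5.1 adds a press release, flyers, and paid and unpaid social media: "The application of the social media recruitment methods will allow researchers to reach a larger cohort in the UK".

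**Adjustment.** The conditional logistic model in section 9.2.3 is fitted "adjusting for stage and histology and other potentially confounding variables collected from the risk factor questionnaire".

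**Questionnaire content.** Section 6.1.1 begins: "The well-established risk factors include ethnicity, marital status, body mass index, age at menarche, menopausal status, age at menopause, parity". It continues with reproductive and medical history, vaping and smoking. Section 6.1.3 adds stores used, loyalty cards held and how often they are used, and household size, which is collected expressly for adjustment. Section 6.1.4 adds COVID-19 status. Region, home postcode, education, income, occupation and area deprivation are not listed.

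**Location data.** Under section 7.7 the retailers report "when (i.e. date of purchase) and where they were purchased (i.e. store postcode" for the items bought, but not the home postcode. Controls supply a utility bill for identity checks. It is deleted once identity is confirmed and the purchase history is returned (section 9.1.6a).

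**Matching.** Sections 1.2 and 3 call the study matched. No matching factor is named.

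**The concern.** The two groups are sampled by different routes. Where a case lives depends on which clinics take part. Where a control lives depends on who sees the publicity and volunteers. The exposure is purchasing, which plausibly varies with product range, prices, local income and shop closures. The listed covariates are mainly risk factors for ovarian cancer, not determinants of shopping.

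If the mix of areas differs between groups, part of any purchasing difference could be a difference between areas. The primary result is the time before diagnosis at which cases and controls become significantly different. The secondary results are an alert threshold and its predictive values. All three rest on the same case-control contrast, so all three could be biased. The bias could create a difference, enlarge one or hide one.

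**Working it through.** **Step 1. Can the model as written adjust for place?** Section 9.2.3 confines the further confounders to those "other potentially confounding variables collected from the risk factor questionnaire". None of the items listed in sections 6.1.1 to 6.1.4 measures place or socioeconomic position directly. Ethnicity, marital status, smoking, household size and stores used are indirect correlates. The store postcode is retailer data, not questionnaire data, so the wording of 9.2.3 does not reach it, and 9.2.1 to 9.2.8 do not mention it.

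**Step 2. How large could the effect be?** The plan gives no significance level, power, effect size or purchase rate, so it has no figure to reproduce. What follows is an illustration on assumed inputs.

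Inputs: 500 cases and 500 controls (section 3). Assumed: two-sided 5% test, two area types A and B, a yes/no indicator of high purchasing of symptom products, no true case-control difference within an area type, and an unmatched comparison.

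Formulas, with s the share of a group living in A, and r_A and r_B the proportions of high purchasers:

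- p = s × r_A + (1 − s) × r_B, giving p1 for cases and p0 for controls
- OR = [p1/(1 − p1)] / [p0/(1 − p0)]
- SE(ln OR) = √[1/(500 p1) + 1/(500(1 − p1)) + 1/(500 p0) + 1/(500(1 − p0))]
- z = ln OR / SE
- false-positive rate = Φ(z − 1.96) + Φ(−z − 1.96)

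Two 20-point gaps (s = 30% for cases and 50% for controls; r_A = 40%, r_B = 60%):

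- p1 = 0.3 × 0.4 + 0.7 × 0.6 = 0.54
- p0 = 0.5 × 0.4 + 0.5 × 0.6 = 0.50
- OR = (0.54/0.46)/(0.50/0.50) = 1.174
- SE = √(1/270 + 1/230 + 1/250 + 1/250) = 0.127
- z = 0.160/0.127 = 1.27; false-positive rate = 24.4%

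| Share in A, cases v controls | High purchasers, A v B | p1 v p0 | OR | False-positive rate per window |
|---|---|---|---|---|
| 30% v 50% | 40% v 60% | 0.54 v 0.50 | 1.174 | 24.4% |
| 30% v 50% | 45% v 55% | 0.52 v 0.50 | 1.083 | 9.7% |
| 40% v 50% | 45% v 55% | 0.51 v 0.50 | 1.041 | 6.2% |

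Swapping the two groups' shares in the top row gives OR = 1/1.174 = 0.852 with the same 24.4%, so the direction depends on which group lives where.

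A second set of assumed inputs shows how far the answer depends on the assumptions. With 60% to 90% of cases against 50% of controls in one area type, and purchase rates of 25% to 40% there against 20% elsewhere, a pooled two-proportion test gives odds ratios of 1.03 to 1.43 and false-positive rates of 5.4% to 76%.

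**Step 3. Which baseline window could carry an area variable?** Purchase data end at recruitment and go back at most 6 years (section 7.7). Cases may be recruited up to 2 years after diagnosis (section 4.2). At that limit, a full record holds 6 − 2 = 4 years before diagnosis. A 36-month record holds 36 − 24 = 12 months before diagnosis, so its earliest 12 months are the year for which section 6.1.2 asks about symptoms. In a 24-month record everything falls after diagnosis. The window must therefore be fixed relative to diagnosis, not to the start of each record.

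**The case against.** - **The geographic gap is not shown.** A reader might infer that cases come from a few places unlike the rest of the UK. The documents do not support that. Section 5 says the clinics are around the UK, and the site list (Part C, Appendix 3) is not in the text available for review. The gap may be small.
- **Area matching might be intended.** The design is called matched and the model is conditional. With no matching factor named, area matching is neither provided for nor excluded.
- **Social position is not wholly unmeasured.** A reader might infer that nothing collected bears on it. Household size, ethnicity, marital status, smoking and stores used carry some information. The list in 6.1.1 may also be a summary, and the questionnaire itself is not in the text. The supportable statement is that no direct measure is listed.
- **Other location data may exist.** Identity documents are checked against the consent form, which is not in the text. Store postcode is the only location variable described for both groups, but it may not be the only one held.
- **The illustration is simple.** It models a constant offset. Such an offset would also appear years before diagnosis, where it could be recognised as unrelated to the disease. Changes in local shopping over time would be harder to recognise, but no such scenario was computed. The yes/no indicator may also differ from the plan's purchase proportion, which is undefined.

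These objections limit how large and how certain the problem is. They do not remove the gap in section 9.2.3, and they do not give the store postcode a use.

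**Conclusion.** The concern holds as a gap in planned confounder control. The groups are recruited by different geographic routes, the confounders in 9.2.3 are confined to a questionnaire with no listed direct measure of place or socioeconomic position, no matching factor is named, and a location variable supplied with each purchase goes unused. If the groups differ by area, the divergence time and alert threshold could be biased in either direction.

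The size cannot be estimated from the documents. The 6% to 24% per window rests on 500 per group, a two-sided 5% test, no true effect, constant area differences and assumed gaps of 10 to 20 points. It should not be read as the expected error rate. If the groups are alike by area, the effect is negligible. The documents do not show that bias is present; they show that the plan has no stated means of detecting or reducing it.

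**What to change.** Add to section 9.2.3, in substance:

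- Region and small-area deprivation rank will be derived from the postcode of each woman's most-used store in a fixed baseline window that ends well before diagnosis (for controls, before the matched index date). Women with no purchases in that window are flagged as missing.
- Both variables enter the conditional logistic model, or region is used as a matching factor.
- Both are tabulated by case status, so that the report shows whether the groups differ by area.
- One sensitivity analysis is limited to controls whose main store lies in a region with a recruiting site.

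The window limits must be stated. The control index date must be defined too, because section 9.2 does not give one.

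**Cost.** SAP wording, a postcode look-up, two covariates (or one matching factor) and one extra analysis. No new participant data or contact is needed.

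**Limits.** Store area is only a proxy for home area and for a woman's own socioeconomic position, so selection among web volunteers will remain in part. Women with short records will have no baseline value.
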